NNRTI	Non-nucleoside Reverse Transcriptase Inhibitor
NOAEL	No Adverse Effect Level
PCR	Polymerase Chain Reaction
PID	Participant Identification
PMTCT	Prevention of Mother-to-Child Transmission of HIV
PEP	Post-Exposure Prophylaxis
PT	Preferred Term
RNA	Ribonucleic Acid
RPR	Rapid Plasma Reagins
RT	Reverse transcriptase
SAE	Serious Adverse Event
SAP	Statistical Analysis Plan

SCR-ID	Screening Identification
SOC	System Organ Class
SOM	Study Operations Manual
SOP	Standard Operating Procedure
STI	Sexually Transmitted Infection
TEAE	Treatment Emergent Adverse Event
TPHA	Treponema Pallidum Haemagglutination Test
TPPA	Treponema Pallidum Particle Agglutination Assay
TV	Trichomonas Vaginalis
UNAIDS	Joint United Nations Programme on HIV/AIDS
WHO	World Health Organization

PROTOCOL SYNOPSIS IPM 032

A FOLLOW-ON, OPEN-LABEL TRIAL TO ASSESS CONTINUED SAFETY OF AND ADHERENCE TO THE DAPIVIRINE (25 mg) VAGINAL RING-004 IN HEALTHY, HIV-NEGATIVE WOMEN

BACKGROUND: The Phase III clinical program of Dapivirine Vaginal Ring-004, containing 25 mg of dapivirine, consists of the MTN-020 and IPM 027 clinical trials. These trials are conducted in South Africa, Uganda, Zimbabwe and Malawi, to assess the safety and efficacy of the Dapivirine Vaginal Ring-004 in preventing the acquisition of HIV-1 infection through male to female transmission in healthy, HIV-negative women.

IPM 032, a Phase IIIb follow-on trial to IPM 027, has been designed as an open-label clinical trial to collect additional safety data and establish adherence to ring use of the Dapivirine (25 mg) Vaginal Ring-004 in healthy, HIV-negative women with monthly (at least one to a maximum of three months) followed by 3-monthly research centre follow-up visits over 12 months. The safety results and the level of efficacy observed in IPM 027 and MTN-020 will be communicated to the relevant local and international regulatory authorities, IRBs/IECs, community representatives, participants and key stakeholders, as appropriate, before activation of IPM 032.

IPM 032 will be an open-label clinical trial to assess the continued safety of and adherence to the Dapivirine Vaginal Ring-004, inserted monthly in healthy, HIV-negative women.

OBJECTIVES: **The Primary Trial Objectives are:**

1. To assess the safety profile of the 25 mg Dapivirine Vaginal Ring-004, when inserted at monthly intervals, in an open-label trial
2. To assess adherence to the use of the 25 mg Dapivirine Vaginal Ring-004 inserted at monthly intervals, in an open-label trial

The Secondary Trial Objectives are:

1. To assess the incidence of HIV-1 seroconversion
2. To assess the frequency of HIV-1 drug resistance in women who acquire HIV-1 infection

The Exploratory Trial Objectives are:

1. To assess the feasibility of 3-monthly follow-up visits, as a possible schedule for post-licensure vaginal ring clinical follow-up
2. To explore the correlation between drug concentrations and results from the visual inspection of the returned vaginal rings by research staff between the monthly and 3-monthly research centre follow-up schedules
3. To determine the proportion of participants electing to undergo HIV rapid tests at the research centres between scheduled 3-monthly visits

ENDPOINTS AND ASSESSMENTS:

The primary endpoints are:

1. Safety
 - All Adverse Events (AEs) assessed by the investigator to be related to the Dapivirine Vaginal Ring-004
 - All Grade 3 and 4 AEs
 - All Serious Adverse Events (SAEs)
2. Adherence
 - Residual amounts of dapivirine in returned rings; and/or dapivirine concentrations in plasma and/or dapivirine concentrations in vaginal fluid

The primary endpoints will be assessed through:

1. Safety
 - All product-related AEs, Grade 3 or 4 AEs, SAEs, physical examination, gynaecological assessments, including pelvic/speculum examination, laboratory tests and other indicated investigations
2. Adherence
 - Determined dapivirine residual amounts in returned used vaginal rings and/or
 - Measured concentrations of dapivirine in plasma and/or
 - Measured concentrations of dapivirine in vaginal fluids

The secondary endpoints are:

- The HIV-1 seroconversion rate per 100 woman-years of product use at the end of the vaginal ring use period
- HIV-1 drug resistance mutations among participants who acquire HIV-1 infection

The secondary endpoints will be assessed through:

- Rapid and specialised laboratory testing according to a pre-specified HIV testing algorithm
- Viral genotype resistance testing methods

The exploratory endpoints are:

- Feasibility of 3-monthly clinical follow-up schedule
- Dapivirine residual amounts in returned used vaginal rings and/or dapivirine concentrations in blood and/or vaginal fluid in correlation with results from the visual inspection of the returned used vaginal rings by research staff
- Proportion of participants opting for HIV rapid tests at the research centre between scheduled 3-monthly research centre follow-up visits

The exploratory endpoints will be assessed through:

- Participant report of feasibility regarding a 3-monthly clinical follow-up schedule (Participant Questionnaire)
- Number of women opting not to receive two additional rings at the 3-monthly visits
- Proportion of returned rings (used and unused) during the 3-monthly clinical follow-up schedule
- Dapivirine residual amounts in returned used vaginal rings and/or dapivirine concentrations in blood and/or vaginal fluid
- Visual inspection of the returned used vaginal rings by research centre staff
- Number of participants undergoing HIV rapid tests at the research centre between scheduled 3-monthly research centre follow-up visits

TRIAL DESIGN: IPM 032 is a Phase IIIb, multi-centre follow-on open-label trial to evaluate the continued adherence to and safety of the Dapivirine Vaginal Ring-004 inserted at monthly intervals in healthy, HIV-

negative women who have participated in the IPM 027 Phase III Dapivirine Vaginal Ring-004 trial. All women who have participated in IPM 027 and are HIV-negative at screening for IPM 032 will be eligible. An estimate of approximately 1400 participants will be enrolled.

All participants will attend a research centre follow-up visit one month after enrolment. Following this visit, at investigator's discretion, a participant can continue on a 3-monthly visit schedule. Monthly visits may however be extended up to the first three months of participation. Once the 3-monthly trial visit schedule commences, three rings will be dispensed to the participant. One ring will be self-inserted at the research centre and two additional rings will be dispensed for the participant to take home, or dispensing will take place as arranged with the participant.

TRIAL DURATION: Each participant will engage in the screening process for up to 45 days prior to enrolment and will use the Dapivirine Vaginal Ring-004 for a period of up to 12 months. IPM will have the option to extend this trial period. Accrual will take place over approximately 6 months and those participants who are enrolled more than 6 months after the onset of the study site's accrual period may have a shortened follow-up period.

Each participant will have an exit visit 1-2 months after ring discontinuation, to assess safety and identify HIV seroconversions after product discontinuation.

POPULATION AND SAMPLE SIZE:

Approximately 1400 HIV-negative women who have participated in the IPM 027 Phase III Dapivirine Vaginal Ring-004 trial, who understand the trial, and can provide informed consent, are expected to enrol in this open-label trial.

INCLUSION CRITERIA:

Women must meet all of the following criteria to be eligible for trial enrolment:

1. Previously enrolled in the IPM 027 trial
2. Available for all visits and consent to follow all procedures scheduled for the trial
3. Using an effective method of contraception at the Enrolment Visit, and intending to use an effective contraceptive method for the duration of trial participation, unless post-menopausal with no history of menses for one year prior to screening
4. HIV-negative as determined by the HIV algorithm applied at Screening/Pre-Enrolment

5. Willing to refrain from participation in another research trial using drugs, vaccines, medical devices and microbicides for the duration of the IPM 032 trial
6. Willing to provide adequate locator information for trial retention purposes and be reachable per local standard procedures (e.g. by home visit or telephone; or via family or close neighbour contacts); confidentiality to be maintained

EXCLUSION CRITERIA:

Women who meet any of the following criteria are NOT eligible to enroll in the trial:

1. Investigational product use permanently discontinued in response to an AE (where the AE was considered related to investigational product) or safety-related concern while taking part in the IPM 027 trial
2. Participant self-report of taking post-exposure prophylaxis (PEP) within ≤ 2 months at Screening Visit
Note: Participants may be enrolled after completing the PEP regimen and a negative HIV test was documented at least 2 months prior to screening for IPM 032
3. Currently pregnant, intends to become pregnant, or currently breast-feeding
4. Known drug abuse or alcohol dependence in the 12 months prior to screening
5. Participated in another research trial (other than IPM 027) using drugs, medical devices, microbicides or oral pre-exposure prophylaxis agents within 30 days prior to screening
6. Any new illness or condition(s), chronic condition(s) or abnormal laboratory finding(s) that, in the opinion of the investigator, might put the participant at risk, or interfere with the trial objectives or the participant's adherence to trial requirements

METHODS:

Screening Visit:

Potential participants who are HIV-negative, who participated in IPM 027 and who provide informed consent will be invited to screen for the trial and to enrol in the open-label follow-on study. After informed consent is obtained, a SCR-ID number will be assigned to each potential participant for identification purposes and the potential participant will be screened to assess eligibility for the study. A comprehension checklist will be used to support the informed consent process.

At screening, potential participants will provide information on inclusion and exclusion criteria, including locator and basic

menses information, demographic information, and medical and concomitant medication history. Each potential participant will receive a general physical examination and pelvic examination.

All potential participants will be provided with HIV/STI risk-reduction counselling (including provision of male condoms, should participants wish to receive them), contraceptive counselling and HIV pre- and post-test counselling. Contraceptives will be provided if necessary, as well as treatment and/or referral for sexually transmitted infections (STIs) and other findings as necessary. Safety laboratory assessments, urine dipstick analysis (microscopy only if clinically indicated), cervical sample collection for cytology and testing for pregnancy, HIV, STIs, and syphilis will be performed. Blood samples for HIV-1 RNA PCR and HIV viral genotype resistance testing will be collected and stored for retrospective testing subsequent to a confirmed HIV-1 seroconversion.

Enrolment Visit:

At the Enrolment Visit, potential participants will provide information on inclusion and exclusion criteria, including locator and basic menses information, and medical and concomitant medication history. AEs (post-enrolment) and the occurrence of possible social harms will be assessed.

All potential participants will be provided with HIV/STI risk-reduction counselling (including provision of male condoms, should participants wish to receive them), contraceptive counselling and provision of contraceptives (if necessary), HIV pre- and post-test counselling and vaginal ring adherence counselling. Participants will be provided with feedback on the IPM 027 and MTN-020 trial results. Diary cards will be issued with instructions for completion. Testing for pregnancy and HIV will be performed. Blood samples will be collected for storage, and HIV-1 RNA PCR and HIV viral genotype resistance testing will be performed retrospectively subsequent to confirmed HIV-1 seroconversion.

Eligible women will be assigned a unique PID number. Each participant will be provided with vaginal ring use and storage instructions and instructed to self-insert a newly dispensed vaginal ring.

Trial Visits:

All participants will provide information on concomitant medication, locator details and menses. Participants will receive pre- and post-test HIV counselling; HIV/STI risk reduction counselling; vaginal ring adherence counselling; HIV rapid testing and pregnancy testing. Male condoms will be provided at all visits, should participants wish to receive them, as part of HIV/STI risk reduction

counselling. Contraceptive counselling and contraceptives (if needed) will be provided at all visits. Possible occurrence of social harms will be assessed during research centre visits.

Blood samples will be collected for storage at each trial visit and will be tested retrospectively by HIV-1 RNA PCR and HIV viral genotype resistance testing subsequent to confirmed HIV seroconversion. At the point of HIV seroconversion, vaginal ring use will be discontinued, and in addition, blood samples for viral genotype resistance testing will be collected at the scheduled exit visit, 1-2 months following seroconversion.

Blood and vaginal fluid samples will be collected for possible measurement of dapivirine concentrations. Returned rings will be visually inspected by research centre staff and may also be analysed for residual amounts of dapivirine.

Returned diary cards will be reviewed and new diary cards issued to participants as applicable. Each participant will be asked to complete a Participant Questionnaire at every trial visit. AEs will be assessed at all visits post-enrolment. In addition, if clinically indicated, safety laboratory assessments, urine dipstick analysis (microscopy only if clinically indicated), pelvic examinations, cervical sample collection for cytology, physical examinations and STI tests will be performed. Treatment and/or referral for STIs and other findings may be performed, if required.

At each trial visit, participants will return used vaginal rings and each participant will be instructed to self-insert a newly-dispensed vaginal ring and be provided with vaginal ring use and storage instructions. Two additional rings will be dispensed once participants commence with the 3-monthly trial visit schedule, which the participants should self-insert at monthly intervals, at home, until the next Trial Visit. Participants who prefer not to have additional vaginal rings in their possession may also choose to return and to collect the vaginal rings from the research centre at time intervals suitable to them, providing a new ring is inserted monthly. HIV rapid tests will be offered to participants during these interim visits.

If a participant is unable to attend the next scheduled visit, the investigator or designee could dispense additional ring(s) on a case-by-case basis. All such circumstances must be documented fully by the investigator or designee as described in the IPM 032 Study Operations Manual (SOM). If a participant requires an additional ring at a time other than when they are scheduled to receive one, they will be required to attend the clinic for an interim visit.

Last product use visit (LPUV):

At the last product use visit, participants will return any used/unused rings; report any medical problems, social harms and concomitant medications since the last visit; provide locator and basic menses information; receive pre- and post-test HIV counselling, contraceptive counselling and HIV/STI risk-reduction counselling (including provision of male condoms, should participants wish to receive them); undergo a physical examination as well as a pelvic examination; be tested for STIs, pregnancy and HIV; and may undergo safety laboratory assessments, urine dipstick analysis (microscopy only if clinically indicated) and cervical sample collection for cytology (if no result is evident within the previous year, or abnormal at last cervical cytology). Contraception and STI treatment will be provided or participants will be referred, if needed. Blood samples will be collected for storage, and will be tested retrospectively by HIV-1 RNA PCR and HIV viral genotype resistance testing subsequent to confirmed HIV seroconversion. Blood and vaginal fluid samples may be collected for measurement of dapivirine concentrations. Returned rings will be visually inspected by research centre staff and may also be analysed for residual amounts of dapivirine. Returned diary cards will be reviewed. Participants will be asked to complete a Participant Questionnaire.

Exit visit - 1-2 months after ring discontinuation:

On the day of the scheduled exit visit, participants will return to the research centre to receive results from their STI testing and safety laboratory assessments performed at the last product use visit, if applicable, and receive treatment or referral as needed. AEs, concomitant medications and possible social harms will be recorded at this visit.

Participants will receive pre- and post-test counselling for HIV and undergo HIV testing. HIV/STI risk reduction counselling (including provision of male condoms, should they wish to receive them) and contraceptive counselling will also be provided at the exit visit. Contraception and STI treatment will be provided or the participant will be referred, if needed. The following procedures are not required, but may be conducted if clinically indicated: physical and pelvic examination, cervicovaginal sample collection for STI testing, provision of treatment and/or referral for STIs and other findings, laboratory testing for safety assessments, urine dipstick analysis (microscopy only if clinically indicated) and cervical sample collection for cytology (if no result is evident within the previous year, or abnormal at last cervical cytology).

Blood samples will be collected for storage, and will be tested retrospectively by HIV-1 RNA PCR and HIV viral genotype resistance testing subsequent to confirmed HIV seroconversion.

Participants will then be considered to have completed trial participation.

STATISTICAL CONSIDERATIONS:

Sample Size:

This is an open-label, follow-on trial to IPM 027 to evaluate the safety of and adherence to Dapivirine Vaginal Ring-004, inserted at monthly intervals in healthy, HIV-negative women who have participated in the IPM 027 trial. No formal sample size or power calculations have thus been performed.

It is expected that approximately 70% of the participants enrolled in IPM 027 will participate in this trial. Therefore, a total sample size of approximately 1400 HIV-negative women is anticipated.

Statistical Analyses:

The primary analysis will focus on safety as well as adherence assessments, performed under the intent-to-treat (ITT) principle. As it is possible that the inclusion of non-adherent participants or participants who discontinued from ring use may artificially lower the rates of safety outcomes, additional analyses will be conducted on the per-protocol population, which will include only participants who were adherent to the protocol.

A descriptive analysis of all AEs will be presented in tables and listings. AEs will be summarised by MedDRA System Organ Class (SOC) and Preferred Term (PT). The proportion of participants experiencing adverse events, including the proportion of participants experiencing product-related adverse events, Grade 3 or 4 AEs, or SAEs, will be determined, and presented with corresponding 95% confidence intervals (CIs).

Residual levels of dapivirine in returned rings, and/or plasma and/or vaginal fluid concentrations of dapivirine will be used as measures of adherence to ring use. The data will be listed, summarised and presented graphically. Participants will be categorized as either adherent or non-adherent, based on these measures. The ring residual levels and/or plasma and/or vaginal fluid concentrations of dapivirine associated with non-adherence will be informed by the results from IPM 027, and will be described in detail in the SAP, which will be finalised prior to final database lock. The correlation between the amount of residual dapivirine in the used rings and the corresponding plasma and/or vaginal fluid levels of dapivirine will be explored graphically and summarised descriptively.

For the secondary analysis, the number of HIV-1 seroconversions, the incidence density rate of HIV-1 seroconversion, i.e. HIV-1 seroconversion rate per 100 woman-years of product use at the end of the ring use period, as well as a 95% confidence interval for the HIV-1 seroconversion rate per 100 woman-years based on the normal approximation of the Poisson distribution will be presented for each research centre and overall. Kaplan-Meier curves will also be presented, stratified by research centre. The analysis of

HIV-1 drug resistance will be primarily descriptive in nature, and will depend on the pattern of resistance mutations observed in the HIV-1 seroconverters. A frequency tabulation of individual resistance mutations associated with the various classes of antiretrovirals, e.g. Protease Inhibitors, Nucleoside Reverse Transcriptase Inhibitors and Non-nucleoside Reverse Transcriptase Inhibitors, will be produced. The proportion of HIV-1 seroconverters with at least one HIV-1 drug resistant mutation will be presented, with the corresponding 95% CI.

Appropriate statistical analyses of the exploratory endpoints will be performed.

Full details of the planned statistical analyses will be provided in a Statistical Analysis Plan (SAP) that will be finalised before final database lock.

1. Introduction

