Residual levels of dapivirine in returned rings and/or plasma and/or vaginal fluid concentrations of dapivirine will be used as measures of adherence to ring use. The data will be listed, summarised and presented graphically. Participants will be categorized as either adherent or non-adherent, based on these measures. The ring residual levels and/or plasma and/or vaginal fluid concentrations of dapivirine associated with non-adherence will be informed by the results from IPM 027, and will be described in detail in the SAP, which will be finalised prior to final database lock. The correlation between the amount of residual dapivirine in the used rings and the corresponding plasma and/or vaginal fluid levels of dapivirine will be explored graphically and summarised descriptively.

8.4.3. *Secondary Analyses*

8.4.3.1. *Incidence of HIV-1 seroconversion*

The incidence of HIV-1 seroconversions, the incidence density rate of HIV-1 seroconversion, i.e. HIV-1 seroconversion rate per 100 woman-years of product use at the end of the ring use period, as well as a 95% CI for the HIV-1 seroconversion rate per 100 woman-years based on the normal approximation of the Poisson distribution will be presented for each research centre, and overall. Kaplan-Meier curves will be presented, stratified by research centre.

8.4.3.2. *HIV-1 drug resistance*

The analysis of HIV-1 drug resistance will be primarily descriptive in nature, and will depend on the pattern of resistance mutations observed in the HIV-1 seroconverters. The resistance associated mutations observed will be listed by participant, and a frequency tabulation of individual resistance mutations associated with the various

classes of antiretrovirals, e.g. Protease Inhibitors, Nucleoside Reverse Transcriptase Inhibitors and Non-nucleoside Reverse Transcriptase Inhibitors, will be produced. The proportion of HIV-1 seroconverters with at least one HIV-1 drug resistant mutation will be presented, with the corresponding 95% CI.

8.4.4. *Interim Analysis*

No interim analysis is planned for this trial. However, the Sponsor will review the treatment emergent safety data at regular intervals during the conduct of the trial.

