- Analysis 3: All confirmed HIV-1 seroconverters determined to have been HIV-1 infected after enrollment will be considered as infected on product, even in instances where HIV-1 seroconversion and estimated point of infection was determined to be after the last product use visit.
- Analysis 4 (HIV-1 infection rate): Similar to Analysis 1, but based on time to first positive HIV-1 RNA.

All additional analyses will be performed on the m-ITT population.

For the number of participants included in the m-ITT analysis in IPM 032, matching placebo participants will be resampled with replacement from the IPM 027 trial, based on research center, age and STI prevalence at screening. These factors were selected because of their strong association with HIV incidence.

Age categories (18-24, and \geq 25 years) will be used to ensure that a sufficient number of participants are represented in each combination of categories of age, center and STI prevalence at screening (Yes/No). This resampling will be repeated 10 000 times; by ordering the 10 000 incidence rates and taking the 250th and 9750th value, a 95% confidence interval can be established. The placebo ring data of the complete double-blind period of IPM 027 will be used for this simulation.

The incidence of HIV-1 seroconversions, the incidence density rate of HIV-1 seroconversion (*i.e.* HIV-1 seroconversion rate per 100 person-years of product use at the end of the ring use period) as well as a 95% confidence interval for the HIV-1 seroconversion rate per 100 person-years (based on the normal approximation of the Poisson distribution) may be presented for the simulated placebo and treatment arm, overall and for each research centre. Similarly, the incidence of HIV-1 seroconversions, the incidence density rate and 95% CI will be presented by visit schedule (A, B or C) and overall. The 95% CI will be calculated using the formula below:

$$95\% \text{ confidence interval} = [(n/PY) \pm 1.96 \times (\sqrt{n/PY} / PY)] \times 100$$

where:

n = number of HIV-1 seroconversions

PY = total number of person-years of product use

Kaplan-Meier curves, of time to HIV-1 seroconversion will be presented, overall and by research centre using PROC LIFETEST in SAS®.

The time to event will be calculated as follows:

Time to event (days) = (Date of seroconversion/Censoring Date – Date of first ring use) + 1

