11 CHANGES IN THE PROTOCOL-PLANNED ANALYSES

There are no changes to the protocol-planned analyses.

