Table 14.3.7.5

Analysis 1, HIV-1 Seroconversion Rate per 100 Person-Years of Product Use

Population: m-ITT

	Statistic	IPM 027 Dapivirine (N=XXX)	IPM 027 Placebo (N=XXX)	IPM 032 Overall (N=XXX)
Number of confirmed HIV-1 seroconversions on IP	n (%) ^a	X (X.X)	X (X.X)	X (X.X)
Total number of person-years	PY	XXX	XXX	XXX
Seroconversion rate (per 100 person-years)	n/PY	XX.X	XX.X	XX.X
95% CI for seroconversion-rate (per 100 person-years)	95% CI ^b	XX.X, XX.X	XX.X, XX.X	XX.X, XX.X

Programmers Note: Please repeat the table for the PP population

CI = Confidence interval; HIV-1 = Human immunodeficiency virus type 1; IP = Investigational product

^a Percentages are calculated out of the number of participants in the applicable population per IPM 027 treatment

^b 95% CI calculated as $[(n/PY) \pm 1.96 \times ([n/PY] / PY)^{1/2}] \times 100$; where n = number of HIV seroconversions and PY = total number of person-years of product use calculated as PY = (Date of last ring removal – Date of first ring insertion + 1)/365.25

Table 14.3.7.6
 Analysis 2, HIV-1 Seroconversion Rate per 100 Person-Years of Product Use
 m-ITT

	Statistic	IPM 027 Dapivirine (N=XXX)	IPM 027 Placebo (N=XXX)	IPM 032 Overall (N=XXX)
Number of confirmed HIV-1 seroconversions on IP	n (%) ^a	X (X.X)	X (X.X)	X (X.X)
Total number of person-years	PY	XXX	XXX	XXX
Seroconversion rate (per 100 person-years)	n/PY	XX.X	XX.X	XX.X
95% CI for seroconversion-rate (per 100 person-years)	95% CI ^b	XX.X, XX.X	XX.X, XX.X	XX.X, XX.X

CI = Confidence interval; HIV-1 = Human immunodeficiency virus type 1; IP = Investigational product

^a Percentages are calculated out of the number of participants in the m-ITT population per IPM 027 treatment

^b 95% CI calculated as $[(n/PY) \pm 1.96 \times ([n/PY] / PY)^{1/2}] \times 100$; where n = number of HIV seroconversions and PY = total number of person-years of product use calculated as PY = (Date of last ring removal – Date of first ring insertion + 1)/365.25

In instances where it cannot be ruled out that HIV-1 infection may have occurred during IP use in case the HIV RNA test has detectable levels at the next visit after ring use, such participants will be considered as being seroconverted

Table 14.3.7.7
 Analysis 3, HIV-1 Seroconversion Rate per 100 Person-Years of Product Use
 m-ITT

Statistic	IPM 027 Dapivirine (N=XXX)	IPM 027 Placebo (N=XXX)	IPM 032 Overall (N=XXX)
Number of confirmed HIV-1 seroconversions on IP	n (%) ^a	X (X.X)	X (X.X)

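### The HIV-1 seroconversion rate and CI by research centre, promised in the protocol, become optional in the SAP, have no place in the rate tables, and are not declared as a change

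*Protocol*

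**What the plan says.** The protocol makes the commitment twice. The synopsis, under Statistical Analyses, says that the 95% CI for the rate, "based on the normal approximation of the Poisson distribution will be presented for each research centre and overall". Section 8.4.3.1 repeats it: "based on the normal approximation of the Poisson distribution will be presented for each research centre, and overall".

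SAP 9.3.1 lists the same quantities (incidence, rate per 100 person-years, 95% CI) but says that they "may be presented for the simulated placebo and treatment arm, overall and for each research centre". The next sentence uses firm wording for a different split: "the incidence density rate and 95% CI will be presented by visit schedule (A, B or C) and overall". The same section says that, for the comparator, "matching placebo participants will be resampled with replacement from the IPM 027 trial, based on research center, age and STI prevalence at screening", and adds: "These factors were selected because of their strong association with HIV incidence".

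The shells for Analyses 1 to 4 (Tables 14.3.7.5 to 14.3.7.8) have three columns: IPM 027 Dapivirine, IPM 027 Placebo and IPM 032 Overall. The footnote to Table 14.3.7.5 matches that layout: "Percentages are calculated out of the number of participants in the applicable population per IPM 027 treatment". The only repeat instruction in this group is for the PP population. SAP 11 states: "There are no changes to the protocol-planned analyses".

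**The concern.** Following the SAP as written could drop a protocol-specified secondary output without anyone having declared it. An analyst who reads 9.3.1 may treat the centre breakdown as optional. A programmer who builds the shells would have no reason to produce it. A reader of SAP 11 would believe that nothing had changed.

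The output has a use. The trial has no concurrent control, and the SAP itself counts centre among three factors that it links strongly to HIV incidence. IPM 027 ran at seven centres (protocol 1.4.2), whereas the IPM 032 shells name six, so the centre mix is not the same as in the parent trial. Centre rates let a reader see how far a pooled rate depends on which centres contributed the follow-up.

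**Working it through.** The plan states no figure to reproduce here, so the main check sets the texts side by side.

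1. **Commitment.** Protocol synopsis and 8.4.3.1: rate and CI by centre, firm.
2. **SAP text.** 9.3.1: by-centre rate and CI, optional. SAP 6.6 has a general rule that descriptive statistics are shown overall and by centre. It does not name this output.
3. **Rate shells.** 14.3.7.5 to 14.3.7.8: no centre columns and no instruction to repeat by centre. The list of tables shows no other HIV-1 rate table.
4. **Other by-centre HIV-1 output.**
   - Kaplan-Meier curves of time to seroconversion, firm in 9.3.1, though SAP 6.5 adds that curves by centre are produced if possible.
   - Table 14.1.2.1 has centre columns and is repeated for women who seroconverted on product use, so it gives on-product counts per centre.
   - Table 14.3.7.4 gives seroconverters as n (%) per centre and, for the pregnancy rate, person-years per centre, by the same formula as the HIV-1 rate tables.
   - Both tables use the safety population. The m-ITT population removes women found to be infected at enrolment.
5. **Declared changes.** SAP 11: none.

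A reader could thus come close to a centre rate by dividing a count in one table by person-years in another. The m-ITT rate and its CI by centre appear nowhere.

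The second check is whether the planned interval would serve at centre level. The formula in the rate-table footnotes is 100 × [n/PY ± 1.96 × √((n/PY)/PY)], which equals 100 × (n ± 1.96√n)/PY. Its lower limit is negative when √n < 1.96, that is, when n < 1.96² = 3.84, so for 1, 2 or 3 events whatever the person-time. At n = 0 its width is zero. The exact Poisson limits are 100 × χ²(0.025; 2n)/(2PY) and 100 × χ²(0.975; 2n+2)/(2PY).

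The documents give no event counts or person-years by centre. As an assumption, take 1,400 woman-years (about 1,400 women for one year each) split evenly over the six centres in the shells: 1,400/6 = 233.3 each.

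| Events | Rate per 100 | Normal 95% CI | Exact 95% CI |
|---|---|---|---|
| 0 | 0.00 | 0.00 to 0.00 | 0.00 to 1.58 |
| 1 | 0.43 | −0.41 to 1.27 | 0.01 to 2.39 |
| 2 | 0.86 | −0.33 to 2.05 | 0.10 to 3.10 |
| 3 | 1.29 | −0.17 to 2.74 | 0.27 to 3.76 |
| 4 | 1.71 | 0.03 to 3.39 | 0.47 to 4.39 |
| 6 | 2.57 | 0.51 to 4.63 | 0.94 to 5.60 |
| 10 | 4.29 | 1.63 to 6.94 | 2.06 to 7.88 |

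Halving the person-time doubles every rate and limit and leaves the sign pattern as it is. Comparing the 1-event and 10-event rows is purely illustrative: the spread between them is put in by the choice of counts and is not a forecast.

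**The case against.** The strongest reply is that this is an inconsistency of wording and layout, with most of the substance kept. SAP 9.3.1 still names the by-centre rate, and its optional wording may have been aimed mainly at the simulated placebo arm. SAP 6.6 sets a general by-centre rule. SAP 1 calls the appendices supporting material, so a missing column does not override the text. Kaplan-Meier curves by centre account for follow-up time. The centre-mix worry is largely met by the comparator, since the placebo resample is matched on centre, and single-arm centre rates could not separate a ring effect from background incidence anyway. The endpoint is secondary and descriptive, with no test. Exact limits also depart from the protocol that the point asks the SAP to honour.

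Much of this stands. A reader might infer that the by-centre rate has been removed from the plan. The documents do not support that, because 9.3.1 permits it. A reader might also infer that the crude n (%) in Table 14.3.7.4 is the only by-centre HIV-1 figure. That is wrong, given the repeats of Table 14.1.2.1 and the planned curves. The sentence on strong association covers centre, age and STI prevalence together and gives no strength for centre alone.

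What remains is that the sentence, as written, makes the IPM 032 centre rate optional along with the placebo rate. The overall rate is secured by the shells and by the visit-schedule sentence; the centre rate is secured by neither. Survival curves do not give a rate per 100 woman-years with a CI. The departure to exact limits is real and should be declared.

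**Conclusion.** The point holds in this form: a secondary output that the protocol promises twice is optional in the SAP text, absent from the rate shells and not listed as a change, so it is not assured. No shell gives the m-ITT seroconversion rate with its CI by centre.

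The consequence is moderate. The ingredients are largely planned elsewhere, for the safety population, and the centre-matched placebo resample already deals with much of the centre-mix question. The textual finding rests on no numerical assumption. The failure of the normal formula at 0 to 3 events does not depend on person-time, but whether any centre falls in that range is unknown from the documents. The interval values in the table depend on the assumed even split of 1,400 woman-years.

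**What to change.** In SAP 9.3.1, make the by-centre presentation of the IPM 032 rate firm again; the simulated placebo by centre can stay optional. Add a block to Table 14.3.7.5 with one line per centre: events, woman-years, rate per 100 and 95% CI, under the same event and person-time rules as the overall column. Use exact Poisson limits in that block, and record this in SAP 11 as a change from the protocol's normal approximation, with the reason: negative lower limits at 1 to 3 events and zero width at none.

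The cost is one table block from data already in the analysis set. The drawback is imprecision. With the footnote formula and the same assumption, 24 events overall give 1.03 to 2.40 (width 1.37), while 4 events in one centre give 0.03 to 3.39 (width 3.36), about 2.5 times as wide. The block should be read as description and not used to rank centres.
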